Participants were randomized in 1:1 sequence using a random number generator (randomizer.org). Two hundred participant ID numbers (1-200) were randomized prior to study commencement and assigned to patients who were prescreened. Due to a high number of ineligible participants, an additional 100 ID numbers (201-300) were randomized during the recruitment process. Participants retained the same ID number throughout, regardless of their eligibility, to simplify the process for administrative staff at the clinics. Participants were blind to their condition, but physicians and administrative staff were not blind to participant condition. Physicians were not blind to participant condition because they were responsible for delivering the ACT intervention or standard care. They were thus required to know the participant's condition in order to deliver the adequate treatment. Administrative staff was responsible for providing physicians with this information and organizing study paperwork and thus needed to be aware of participant condition as well.

Physician Training

Physicians were trained in the delivery of the weight loss interventions in a 1-hour Skype training session delivered by a clinical psychology PhD student. During this training session, each physician was taught how to administer the manualized ACT intervention and provided the opportunity to ask questions pertaining to the various skills that they would be required to teach their patients. Copies of the manual were provided to physicians to follow during sessions. Follow-up training sessions were conducted as necessary to ensure treatment fidelity and clarify questions that arose as physicians began delivering the interventions.

Intervention

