Participants in the standard care condition were provided with diet and exercise counselling and psychoeducation from their physicians over the course of 8 sessions, as was routinely done at the clinic. Physicians were responsible for facilitating this counselling at their discretion, and thus what “standard care” entailed differed based on the physician who was administering it. However, standard care did not involve any targeted intervention to reduce emotional eating. Thus, in addition to standard care, participants in the ACT condition were taught techniques to reduce their emotional eating. All sessions were approximately 5-10 minutes in length and weight was assessed at each visit. Three overarching skills were taught over the course of the ACT intervention: (1) values clarification and commitment, (2) metacognitive awareness, and (3) distress tolerance. ACT participants were first taught values clarification and commitment techniques, where they reflected on their reasons for losing weight and how this would improve their quality of life. Participants were taught the BOLD technique (Breathe, Observe sensations, Listen to values, Decide on actions that are in line with values) to use their values to make discussions pertaining to avoiding emotional eating (Ciarrochi, Bailey, & Harris, 2013). Next, participants were introduced to the concept of metacognitive awareness, or recognizing and identifying one’s thoughts, feelings, and emotions. Specifically, participants were trained in mindful eating, in order to increase awareness of hunger and satiety cues and avoid eating when not physically hungry (Kristeller & Wolever, 2011). Lastly, participants were taught to increase distress tolerance in the face of negative emotions that typically led to emotional overeating. Participants were taught acceptance techniques (dropping the rope, urge surfing) to use when experiencing triggering emotions or cravings (Bowen & Marlatt, 2009). An

intervention summary can be found in Table 1 and the intervention manual is available upon request.

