Throughout the sessions, physicians formed if-then plans with the patients to specify how to habitually use the ACT techniques to reduce emotional eating in their everyday lives. At the end of each session, participants were given a one-page homework sheet that asked them to monitor their behavior and their use of the ACT techniques during the week. Participants were instructed to bring the homework back with them for the next session so that it could be reviewed with their physician.

Measures

Demographics. At baseline, participants reported basic demographic information including gender, age, English fluency, ethnicity, marital status, educational attainment, employment status, household income, and whether or not they smoked.

Anthropomorphic measures. Weight was measured at each of the eight sessions (primary outcome). Participant body fat percentage was assessed and recorded by their physician at baseline and at completion of the eight sessions (secondary outcome).

Emotional, restrained, and external eating. Participants were pre-screened for emotional eating using the Dutch Eating Behavior Questionnaire (DEBQ; van Strien et al., 1986). The DEBQ is a 33-item questionnaire that assesses three dimensions of eating behaviors: emotional eating (primary outcome), restrained eating (secondary outcome), and external eating (secondary outcome). The emotional eating subscale assesses the reported desire to eat under specific negative emotional conditions such as stress, anxiety, and depression. The DEBQ has high internal consistency and factorial validity (van Strien et al., 1986). The DEBQ was administered again post-intervention.

Distress tolerance. The Distress Tolerance Scale (DTS; Simons & Gaher, 2005), a brief self-report questionnaire that assesses one's ability to tolerate distressing emotions, was completed at baseline and post-intervention (secondary outcome). The scale is made up of items that assess the dimensions of distress tolerance, absorption, appraisal, and regulation. The DTS has high reliability and high discriminant, convergent, and criterion validity (Leyro, Bernstein, Vujanovic, McLeish, & Zvolensky, 2011; Simons & Gaher, 2005).

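### Body fat is read and recorded by the treating physician, who knows the arm, and the plan describes no safeguard; for weight the measurer is not stated

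*Combined protocol and SAP*

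**What the plan says.** **Body fat.** Under Measures, Anthropomorphic measures: "Participant body fat percentage was assessed and recorded by their physician at baseline and at completion of the eight sessions (secondary outcome").

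**Who knows the arm.** Randomization and Blinding states: "Participants were blind to their condition, but physicians and administrative staff were not blind to participant condition". It gives a reason for each group. For physicians: "Physicians were not blind to participant condition because they were responsible for delivering the ACT intervention or standard care". For the other group: "Administrative staff was responsible for providing physicians with this information and organizing study paperwork and thus needed to be aware of participant condition as well".

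**Weight.** The same Measures paragraph says "Weight was measured at each of the eight sessions (primary outcome"), and the Intervention section says "All sessions were approximately 5-10 minutes in length and weight was assessed at each visit". Neither says who takes or records the reading.

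**Use in the analysis.** Data Analysis puts the anthropomorphic outcomes into a 2 x 2 (Condition by Time) repeated measures MANOVA on Baseline and Session 8, with t-tests to follow as needed.

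For either measure, the plan mentions no device, rounding rule, duplicate reading, source record or assessor without knowledge of the arm.

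**The concern.** The two reasons given for unblinding concern delivering treatment, passing on the allocation and handling paperwork. Neither is a reason for an outcome to be read or entered with the arm known. For body fat, the plan assigns that task to an unblinded person as a stated rule, so this is more than a missing detail.

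Weight and body fat carry particular weight as evidence here. The other primary outcome, emotional eating on the DEBQ, is self-reported, so a reader will look to the physical measures for objective support. If a reading is repeated, rounded or transcribed differently by arm at one time point and not the other, the difference goes straight into the Condition x Time contrast. For body fat, which has only two readings, the plan describes nothing that would reveal it.

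**Working it through.** The plan gives no figure to reproduce here: no SD, alpha, power or effect size. The check is a comparison of the passages, followed by an illustration.

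**Step 1: set the passages side by side.**

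| Question | Body fat (secondary) | Weight (primary) |
|---|---|---|
| Who measures and records? | The participant's physician (Measures) | Not stated (Measures, Intervention, Study Procedures) |
| Does that person know the arm? | Yes, stated (Randomization and Blinding) | Not stated; both named clinic staff groups do |
| Safeguard described? | None | None |
| Readings | Two | Eight, of which two enter the MANOVA |

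The point is direct for body fat. For weight it is reached by elimination.

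**Step 2: which bias matters.** Let b(arm, time) be the mean recording error in an arm at a time point. The bias in the Condition x Time contrast is

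[b(ACT, Session 8) − b(ACT, Baseline)] − [b(Standard, Session 8) − b(Standard, Baseline)].

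If the error in each arm is the same at both times, both brackets are zero and the contrast is unbiased, even when the two arms' errors differ. Only a change in error that differs between arms matters.

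Whether the arm was known at the Baseline reading therefore matters. ID numbers were randomized before being handed out at prescreening, and assignment followed the ID (Study Procedures; Randomization and Blinding). Staff could have known the arm by then, but the plan does not say when physicians were told.

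**Step 3: illustration of size.** Assumptions: two-sided alpha 0.05, no true effect, and a net bias (the quantity in Step 2) of b SDs of the change score. Sample sizes are the planned 64 per arm (Trial Design) and an assumed 32 per arm. The smaller figure is used because Data Analysis mentions large drop-out without giving a rate. For one outcome with two time points, a t-test on the change is the Condition x Time test. In the normal approximation,

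rejection rate = Φ(b/√(2/n) − 1.96) + Φ(−b/√(2/n) − 1.96).

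Example: n = 64 and b = 0.2 give √(2/64) = 0.1768 and 0.2/0.1768 = 1.131. The rate is Φ(−0.829) + Φ(−3.091) = 0.2037 + 0.0010 = 20.5%.

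| b (SD of change) | 64 per arm | 32 per arm |
|---|---|---|
| 0 | 5.0% | 5.0% |
| 0.05 | 5.9% | 5.5% |
| 0.1 | 8.7% | 6.9% |
| 0.2 | 20.5% | 12.6% |
| 0.3 | 39.6% | 22.4% |

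In raw units, assume a body-fat change SD of 2 to 3 percentage points and a net bias of 0.5 to 1.0 point. The upper-tail noncentral-t rate then runs from 15.3% (0.5/3) to 80.1% (1/2) at 64 per arm, and from 9.6% to 50.4% at 32. The upper ends pair the largest assumed bias with the smallest assumed SD, a bias of 0.5 SD. For weight with an assumed change SD of 4 kg, a bias of 0.5 kg gives 10.4% and 1 kg gives 28.9% at 64 per arm.

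These rates show how sensitive the test would be to a bias. They do not show that one exists. They describe the single-outcome test, not the joint MANOVA that comes first.

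**The case against.** The strongest reply is that this is a pilot run by routine clinic physicians, that the plan openly says who is unblinded and why, and that scales and body-fat devices leave little room for judgement. On this view the point is only a request for fuller reporting. Several parts of the reply stand:

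- Silence about a device is not evidence that none was used. An automatic device would limit reading error, though not selective repeats, rounding or transcription.
- A reading habit that is constant over time cancels in the contrast (Step 2).
- Weight is taken at all eight sessions, so an isolated shift at Session 8 could be compared with earlier readings. That would not reveal a bias that builds up across sessions, and it does not help body fat.
- The documents state no stake of the physicians in either arm, so no direction of bias can be assumed.

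A reader might infer more: that both physical outcomes were unprotected, that weight was also read by an unblinded person, or that the results are biased toward ACT. The documents support none of these. They describe no protection, which is not the same as showing there was none. They do not name the person who measured weight. They contain no evidence of any recording difference.

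Other parts of the reply do not stand. Participant blinding does not protect a staff reading. Pilot status does not remove the concern, because weight is named a primary outcome and the arms are compared by formal tests. Disclosing that physicians are unblinded explains how treatment was delivered, but does not deal with their recording an outcome.

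**Conclusion.** The point holds for body fat as a stated feature of the design: an unblinded treating physician assesses and records it at both time points, and the plan describes no safeguard. For weight, the supportable finding is that the measurer and that person's knowledge of the arm are not stated. Concern about unblinded recording of weight is a reasonable inference and no more.

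The effect on the Condition x Time contrast is unknown in size and direction, and is zero for any recording habit that stays constant from Baseline to Session 8. The rejection rates rest wholly on assumed shifts and SDs. This is a worthwhile, inexpensive improvement and gives no ground for saying that the trial's results are biased.

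**What to change.** 1. At Baseline and Session 8, measure weight and body fat before any session content, with the same device and rounding rule in both arms.
2. Keep the first device reading as the source record (printout, export or photo), and log a reason for any repeat.
3. Have a research team member who does not hold the ID-to-arm list enter the values from that record. Labelling the record with the ID alone does not mask it, because assignment follows the ID.
4. If body fat is not a device reading, or no source record exists, report it as unblinded and descriptive, and do not use it to support an ACT effect.
5. State who measured weight and whether they knew the arm.

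**Cost.** A little clinic handling time at two visits; no new staff or patients. Items 4 and 5 need only reporting and still apply where data are already collected. The physician still takes the reading, so the change reduces rounding and transcription bias but does not remove all assessor bias.

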An ACT-Based Physician-Delivered Weight Loss Intervention

Study Protocol

[name], [name], & [name]

July 13, 2016

Study Protocol

The study was approved by the Research Ethics Board (REB-II) at McGill University (Montreal, Canada). Participants provided written informed consent prior to commencing the intervention.

Trial Design

The present study was a two-arm pilot randomized controlled trial conducted from May 7, 2016 to March 7, 2018. Participants were randomized to eight sessions of either an ACT-based intervention aimed at reducing emotional eating or standard care, which involved diet and exercise counselling. All outcomes were assessed at baseline and post-intervention. The present study aimed to recruit 128 participants (64 per condition), similar to the trial protocol outlined by [name] et al. (2014).

Participants

Participants were adults over the age of 18 with overweight or obesity who were seeking treatment for weight loss at a clinic in Toronto, Ontario. Only participants considered to be emotional eaters, as assessed by a score of 3.25 or higher on the Dutch Eating Behavior Questionnaire (DEBQ), were recruited for the study (van Strien, Herman, Anschutz, Engels, & de Weerth, 2012). In addition, participants who did not speak, write, and read in English fluently were excluded from the study, as well as those who were pregnant.

Study Procedures

Participants were recruited upon initial registration at the weight loss clinic. Those who expressed interest to participate were assigned a participant ID number and asked to complete a brief prescreen questionnaire to determine their eligibility based on the criteria described above. Eligible participants were randomly assigned to either the ACT intervention or control condition

based on the ID number they had initially received. Participants completed a battery of questionnaires both baseline and Session 8. Weight was measured every session.

Randomization and Blinding

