All analyses were conducted in SPSS version 24. 2 Two separate 2 (Condition: Standard Care, ACT Intervention) x 2 (Time: Baseline, Session 8) repeated measures MANOVAs were conducted for the anthropomorphic and questionnaire data outlined above, respectively, with follow-up *t*-tests conducted as necessary. Two separate MANOVAs were conducted to not lose data from incomplete cases (i.e., participants who had completed anthropomorphic but not questionnaire data). Independent samples *t*-tests were conducted for treatment satisfaction data collected at Session 8, whereas chi-square tests were conducted to compare recruitment rates, attrition rates, questionnaire completion, and intervention completion time between conditions. Missing data were not imputed because of the large drop out rates: Imputation with small sample sizes and high rates of missingness has been shown to be highly prone to Type I error (McNeish, 2016).

References

- Bowen, S., & Marlatt, A. (2009). Surfing the urge: brief mindfulness-based intervention for college student smokers. *Psychology of Addictive Behaviors, 23*(4), 666-671.
- [name], B., Ivanova, E., Xu, Z., Chamandy, M., Lowensteyn, I., Joseph, L., Luszczynska, A., & Grover, S. (2014). Increasing the effectiveness of the Diabetes Prevention Program through if-then plans: Study protocol for the randomized controlled trial of the McGill CHIP Healthy Weight Program. *BMC Public Health, 14*, 470.
- Kristeller, J., & Wolever, R. Q., (2011). Mindfulness-based eating awareness training for treating binge eating disorder: the conceptual foundation. *Eating Disorders, 19*(1), 49-61.
- Leyro, T. M., Bernstein, A., Vujanovic, A. A., McLeish, A. C., & Zvolensky, M. J. (2011). Distress Tolerance Scale: A confirmatory factor analysis among daily cigarette smokers. *Journal of Psychopathology and Behavioral Assessment, 33*(1), 47-57.
- Simons, J. S., & Gaher, R. M. (2005). The Distress Tolerance Scale: Development and validation of a self-report measure. *Motivation and Emotion, 29*(2), 83-102.

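### Comparing Session 8 outcomes between arms with adjustment for baseline would be more precise than the planned 2 x 2 MANOVAs with unspecified t-tests, and would make the ACT comparison explicit

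*Combined protocol and SAP*

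**What the plan says.** The Data Analysis section describes two repeated measures MANOVAs, one for anthropomorphic and one for questionnaire data. Each crosses Condition with Time: "x 2 (Time: Baseline, Session 8) repeated measures MANOVAs were conducted". Follow-up t-tests are done where needed. Their type is not given (paired within arm, independent at Session 8, or independent on change), nor is what triggers them. No effect is singled out as the ACT comparison and no baseline covariate is mentioned. The same section is specific elsewhere: independent-samples t-tests for treatment satisfaction and between-condition chi-square tests for process measures.

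Other sections that bear on this:

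- Trial Design: "The present study was a two-arm pilot randomized controlled trial", and "All outcomes were assessed at baseline and post-intervention". Treatment satisfaction is the exception. It is collected only after Session 8 and lies outside this point.
- Measures: weight and DEBQ emotional eating are the two primary outcomes.
- Intervention: "Participants in the standard care condition were provided with diet and exercise counselling", and then "Thus, in addition to standard care, participants in the ACT condition were taught techniques to reduce their emotional eating". Both arms therefore receive standard care.
- Participants: only emotional eaters, "as assessed by a score of 3.25 or higher on the Dutch Eating Behavior Questionnaire (DEBQ), were recruited for the study".
- Study Procedures: "Participants completed a battery of questionnaires both baseline and Session 8". Measures mentions the DEBQ first as the prescreen and then says "The DEBQ was administered again post-intervention". Whether the screening score doubles as the baseline score is left open.

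**The concern.** A 2 x 2 repeated measures model gives three effects: Condition, Time and Condition x Time. Only the last compares change between the randomized arms. The Condition main effect averages baseline with Session 8, so it halves any treatment effect. The Time effect pools both arms and says nothing about what ACT adds to standard care.

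Even the right effect does not make full use of the data. With two time points, Condition x Time subtracts baseline with a fixed coefficient of 1. Baseline adjustment (ANCOVA) estimates that coefficient, which lowers the variance whenever the correlation is below 1. For a pilot with heavy drop-out, that precision can be had without collecting anything new.

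**Working it through.** **Inputs.** From the documents: 64 per arm, 1:1 allocation, outcomes at baseline and Session 8. The documents give no alpha, SDs, correlations or completer numbers, so the plan has no figure of its own to reproduce on this point. Assumed: two-sided 5%, r as shown, a Session 8 difference of 0.4 SD, and 20 per arm as an illustration of large drop-out. All results are per outcome, not for the omnibus MANOVA.

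**1. Precision, equal variances (SD = 1 at each time).**

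- Change score, equivalent to Condition x Time: variance 2(1-r).
- ANCOVA: variance 1-r².
- Ratio: (1-r²)/[2(1-r)] = (1+r)/2.

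| r | change | ANCOVA | ratio |
|---|---|---|---|
| 0.3 | 1.40 | 0.91 | 0.65 |
| 0.5 | 1.00 | 0.75 | 0.75 |
| 0.7 | 0.60 | 0.51 | 0.85 |
| 0.95 (weight) | 0.10 | 0.0975 | 0.975 |

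**2. Power.** Noncentral t with noncentrality 0.4/√(2V/n) and df 2n-2 (change) or 2n-3 (ANCOVA), at r = 0.5.

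- n = 64: change 0.4/√(2 × 1.00/64) = 2.26, power 61%. ANCOVA 0.4/√(2 × 0.75/64) = 2.61, power 74%.
- n = 20: 23% against 30%.
- Condition main effect, n = 64: effect 0.4/2 = 0.2 and variance (1+r)/2 = 0.75, power 25%.

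**3. Emotional eating, selected at the DEBQ cut-off.** Put the cut-off at a SD units, with λ = φ(a)/(1-Φ(a)). The variance of the selected screening score is v = 1 + aλ - λ². The scenarios are a = -0.84, -0.36, 0, +0.5 and +1. They are not bounds; -0.36 is what 128 eligible out of 200 would imply.

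- *Screening score is the baseline.* ANCOVA variance 1-r²; change variance (1-r²) + (1-r)²v.
- *Fresh baseline, stable true score, independent error.* True-score variance after selection w = r(1-r) + r²v; baseline variance w + (1-r); correlation ρ = w/(w+1-r); ratio (1+ρ)/2.

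Example at a = +0.5 and r = 0.6: λ = 1.141, v = 0.268.

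- Screening as baseline: change variance 0.64 + 0.16 × 0.268 = 0.683, ratio 0.64/0.683 = 0.937, power at 64 per arm 78% against 80%.
- Fresh baseline: w = 0.24 + 0.36 × 0.268 = 0.337, ρ = 0.337/0.737 = 0.457, ratio 0.729, power 71% against 84%.

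Ratios over all five cut-offs:

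| r | screening is baseline | fresh baseline |
|---|---|---|
| 0.5 | 0.84-0.94 | 0.69-0.72 |
| 0.6 | 0.87-0.95 | 0.72-0.77 |
| 0.7 | 0.91-0.97 | 0.75-0.81 |
| 0.9 | 0.97-0.99 | 0.86-0.92 |

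**4. Validity of the planned interaction.** In simulation with complete data and no effect (selected baselines, r = 0.5, 0.7 and 0.9, 20 to 64 per arm, 8,000 runs per cell), type I error was 0.044-0.056 for Condition x Time and 0.044-0.055 for ANCOVA. The difference is one of precision, not bias.

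**5. Why Time and within-arm tests should be descriptive.** Suppose ACT adds nothing and standard care moves weight by 0.1 SD in both arms (r = 0.95, n = 64). The Time noncentrality is 0.1/√(0.10/128) = 3.58, significant in 94% of trials. The within-ACT paired t-test has 0.1/√(0.10/64) = 2.53, significant in 70%. These figures show what the tests measure. They do not describe a use that the plan states.

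**The case against.** The strongest reply is that the plan already holds a valid test. In a two-arm randomized trial, Condition x Time is the natural reading of a 2 x 2 model. It uses baseline by subtraction, and one sentence naming it would remove the ambiguity. Preferring ANCOVA to a valid change-score comparison is then a choice about precision, worth 2.5% of variance for weight at r = 0.95. This stands, and it limits the point to an improvement rather than the repair of an invalid analysis.

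A reader might infer that the trial took the Time effect or within-arm tests as evidence for ACT. The documents do not say so; they only leave it open. A reader might also infer that regression to the mean in DEBQ scores undermines the comparison. It would arise only if the screening score is the baseline, and it acts on both randomized arms alike, so it does not bias Condition x Time.

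A further objection is multiplicity. Replacing two omnibus tests with about nine univariate ones would give a familywise error of 1 - 0.95⁹ = 37% if they were independent (1 - 0.95² = 10% for the two primaries). This does not defeat the change. The plan already follows its MANOVAs with t-tests and states no correction, and the adjusted estimates take the place of those t-tests. The MANOVA can stay as the omnibus step.

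**Conclusion.** The point holds as one of precision and clarity. Condition x Time is available and valid with complete data, but it is not named, and for every outcome with a baseline it is less precise than a baseline-adjusted comparison. The gain is negligible for weight if r is near 0.95 and material for scales with moderate r: 61% against 74% power at r = 0.5 with 64 per arm. For emotional eating, a primary outcome, it ranges from slight to substantial according to whether the screening DEBQ is the baseline, which the documents do not settle. A blanket statement that the gain there is small, or large, is not supported.

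All sizes rest on assumed correlations, effect size, cut-offs and completer numbers. The stronger claim, that the planned analysis is biased or that efficacy was judged from within-arm change, is not supported by the documents.

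**What to change.** - As the follow-up to the MANOVAs, in place of the unspecified t-tests, estimate for each outcome the between-arm difference at Session 8 adjusted for that outcome's baseline value, with a 95% CI. Name this as the ACT versus standard care comparison, with weight and emotional eating as the primary ones.
- If the MANOVA is kept as an omnibus test, name Condition x Time as the term used.
- Because both arms receive standard care, report Time, the Condition main effect and within-arm changes as descriptive only.
- State whether the screening DEBQ is the baseline DEBQ, and that the comparison is among completers.

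The cost is one degree of freedom per outcome, some rewording and a little more analysis on data already held. It does not address drop-out bias, and it adds no multiplicity rule.

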Mindfulness. At both time points (i.e. baseline, post-intervention) participants completed the Philadelphia Mindfulness Scale (PHLMS; Cardaciotto, Herbert, Forman, Moitra, & Farrow, 2008), a 20-item self-report questionnaire that assesses two components of mindfulness: present-moment awareness and acceptance (secondary outcome). The scale has been shown to have good internal consistency and construct validity (Cardaciotto, Herbert, Forman, Moitra, & Farrow, 2008).

ACT application. At baseline and post-intervention participants filled out a self-report questionnaire designed to assess the extent of the participant's use of ACT strategies to reduce emotional eating (secondary outcome). This questionnaire was developed for the present study to evaluate participants' real world application of the intervention. Participants were asked to indicate their level of agreement on a 5-point scale (1 = strongly agree and 5 = strongly disagree) to prompts such as "My values motivate me to lose weight" and "I am able to accept negative emotions and don't have to eat when I'm feeling bad".

Treatment satisfaction. After the eighth session, participants completed a brief, self-developed questionnaire to assess their overall satisfaction with the intervention. Participants were asked to indicate their level of agreement on a 5-point scale (1 = strongly agree and 5 = strongly disagree). Physicians were also asked to complete a similar questionnaire at various

points throughout the intervention to obtain their input on its feasibility and efficacy of the intervention. Open-ended feedback was also collected from physicians, asking for their suggestions on ways to improve the intervention, and to provide insight on patient dropout/non-responsiveness.

Data Analysis

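### Cheap improvement: make one baseline-adjusted between-arm analysis the main result for each primary outcome, and use the interim weights that the two-time-point MANOVAs leave out

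*Combined protocol and SAP*

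**What the plan says.** The Measures section names two primary outcomes. On weight: "Weight was measured at each of the eight sessions (primary outcome)". On the DEBQ: "emotional eating (primary outcome), restrained eating (secondary outcome), and external eating (secondary outcome)".

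The Data Analysis section states that two "repeated measures MANOVAs were conducted for the anthropomorphic and questionnaire data outlined above, respectively", each with two conditions and two time points (baseline and Session 8), "with follow-up *t*-tests conducted as necessary". Weight therefore sits with body fat percentage. Emotional eating sits with the other questionnaire scores, among them the ACT application measure, a "self-report questionnaire designed to assess the extent of the participant's use of ACT strategies". The models were split so that people with anthropometric but no questionnaire data were kept.

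On missing data: "Missing data were not imputed because of the large drop out rates". No listed analysis uses a weight taken between baseline and Session 8.

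The Trial Design section says that every outcome was assessed at baseline and after the intervention. That fits a Session 8 endpoint.

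**The concern.** A Baseline/Session 8 MANOVA needs both values from each participant. Someone who leaves after, say, Session 5 drops out of the weight analysis entirely, although several weights are on record. Where dropout is described as large, this discards information on a primary outcome.

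The MANOVA result is also a statement about a group of outcomes. A significant Condition x Time effect in the questionnaire model can come from any scale in it, and the effect carries no estimate in DEBQ points. A non-significant one can hide a real effect on emotional eating if the follow-up t-tests run only after a significant omnibus. The plan does not say when they run. It also does not say that they compare the arms: the type is given only for satisfaction ("Independent samples *t*-tests were conducted for treatment satisfaction data collected at Session 8"). At stake are the precision of the weight comparison and the clarity of both primary results.

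**Working it through.** **Inputs.** From the documents: 64 per arm planned, weight at eight sessions, two time points in the model. The documents give no effect size, correlation, alpha, dropout rate or dropout timing for these outcomes, so there is no stated power figure to reproduce. Assumed: d = 0.5 in SDs of change, two-sided 5%, and seven questionnaire scores (three DEBQ scales, one DTS total, two PHLMS components, ACT application). Baseline is taken as Session 1, which leaves seven post-baseline weights, six of them (Sessions 2-7) unused.

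**1. Direct test of one primary outcome.** Noncentral t with noncentrality d√(n/2). At 64 per arm, 0.5√32 = 2.83 gives 80.1% power. At 32 per arm, 0.5√16 = 2.0 gives 50.4%.

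**2. Omnibus-gated t-test.** With two time points, Condition x Time is Hotelling's T² on change scores: T² = (n/2) D′S⁻¹D, where D is the vector of differences in mean change and S the pooled covariance, and F = T²(2n−p−1)/[(2n−2)p] on p and 2n−p−1 df. Success means that the omnibus and the primary outcome's own t-test both reach p < 0.05 (20,000 simulated trials per cell, equal correlation r between scales). Emotional eating moving by 0.5, 64 per arm, power in %:

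| Other six scales | r = 0 | 0.3 | 0.5 | 0.7 |
|---|---|---|---|---|
| none move | 45.8 | 55.6 | 67.0 | 78.3 |
| all move 0.3 | 79.3 | 55.7 | 47.4 | 47.7 |
| all move 0.5 | 80.1 | 76.5 | 67.5 | 57.3 |
| only ACT application moves, 0.5 | 71.7 | 74.4 | 78.6 | 80.1 |

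The range is 46-80% against 80.1% for the direct test. For weight with body fat (p = 2, body fat moving by 0 to 0.5, r = 0 to 0.7) it is 69-79%, a small loss.

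**3. Omnibus driven by a secondary scale.** If only ACT application moves, by 0.5, the noncentrality is λ = (n/2)(0.25)(Σ⁻¹)₁₁, with (Σ⁻¹)₁₁ = [1+(p−2)r]/{(1−r)[1+(p−1)r]}. For p = 7 and n = 64:

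- r = 0: λ = 32 × 0.25 × 1 = 8
- r = 0.3: λ = 8 × 2.5/1.96 = 10.2
- r = 0.7: λ = 8 × 4.5/1.56 = 23.1

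The simulated omnibus is significant in 47.0, 59.3, 76.3 and 95.1% of trials at r = 0, 0.3, 0.5 and 0.7, with emotional eating unchanged. The t-test on emotional eating itself stays at or near 5%.

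**4. Unused weights.** Let π_k be the share of participants with k post-baseline weights and Σ_k the covariance of the first k. Known-covariance information is I = Σ_k π_k Σ_k⁻¹ (each term padded with zeros), and the variance of the Session 8 mean relative to completers is π₇[I⁻¹]₇₇/Σ₇₇. Dropout is 50% and missing at random. Even means 0 to 6 weights equally likely among dropouts. Early means that 40% of dropouts have none, 25% have one and the rest are spread evenly.

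| Dropout | Random walk | Equal corr. 0.5 | Equal corr. 0.8 | AR(1) 0.8 | AR(1) 0.9 |
|---|---|---|---|---|---|
| even | 0.730 | 0.822 | 0.658 | 0.840 | 0.735 |
| early | 0.826 | 0.868 | 0.732 | 0.901 | 0.816 |

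The cut is 16-34% (even) or 10-27% (early). With 32 completers per arm, d = 0.5 becomes 0.5/√0.901 = 0.527 to 0.5/√0.658 = 0.616, and power rises from 50% to about 55-68%. At 30% dropout the cut is 8-20% (even) or 5-15% (early). With an unstructured covariance estimated and 64 randomised per arm at 50% dropout, it is 15-34% and 9-25%.

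**5. ANCOVA for emotional eating.** Let ρ be the unselected pre-post correlation (equal variances before selection) and v the fraction of baseline variance left after selection. ANCOVA variance over change-score variance is (1+ρ)/[(1+ρ)+(1−ρ)v]. With v = 1 this is (1+ρ)/2, or 0.75 and 0.85 at ρ = 0.5 and 0.7: cuts of 25% and 15%. But eligibility was "as assessed by a score of 3.25 or higher on the Dutch Eating Behavior Questionnaire (DEBQ)". If the screening score is the baseline and is normal before selection, v = 1+zh−h², where z is the cut-off and h the normal density at z divided by the eligible share:

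- top 50%: v = 1 − 0.637 = 0.363
- top 20%: v = 1 + 1.178 − 1.959 = 0.219

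The ratios then run from 1.5/(1.5+0.5×0.363) = 0.892 to 1.7/(1.7+0.3×0.219) = 0.963: cuts of 11% down to 4%.

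**The case against.** The plan does give each primary outcome a place: weight in one Condition x Time MANOVA, emotional eating in the other. A reader might infer that no analysis is assigned to them; the text does not support that. Nor do the unused interim weights contradict the plan. Assessment of all outcomes at baseline and post-intervention fits a deliberate Session 8 endpoint, and weighing was a routine part of each visit. This objection stands, and it is why the point is an improvement in efficiency and clarity.

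The gating loss depends on reading the follow-up clause as conditional on a significant omnibus. If the t-tests run regardless, no power is lost. A reader might then say that two unadjusted primary tests demand a Holm correction. The documents set no rule that success on either outcome suffices, and they call the trial a pilot, so adjustment is a trade-off and is not required here.

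A reader might also infer that the follow-ups are within-arm tests, with a 25% chance of a misleading ACT-only result when both arms change equally. The plan does not say so, and 25% is the ceiling of p(1−p), reached near a common change of d = 0.25. At 64 per arm the chance is 10% at d = 0.4 and 2% at d = 0.5.

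Finally, the plan rejects imputation out of concern for Type I error. A likelihood-based mixed model imputes nothing, but the concern has some force. In a simulation with 32 per arm, 50% dropout and plug-in standard errors, Type I error was 5-6% with a t reference based on completers and 6-7% with a normal reference.

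**Conclusion.** The point holds as a cheap improvement. The Condition x Time comparison is valid, but it leaves out recorded weights from people who dropped out, and its omnibus result is neither a test nor an estimate of either primary outcome.

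For weight, the gain is a 16-34% or 10-27% variance cut at an assumed 50% dropout, and 5-20% at 30%. It rests on missing at random and on the assumed correlation patterns holding after baseline adjustment. If those patterns describe raw weights including baseline, the cuts at 50% dropout are 10-27% (even) and 7-17% (early).

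For emotional eating, a direct test avoids a gating loss of between nothing and 34 points (80 − 46), the largest only if the scales are uncorrelated. For weight that loss is small. Baseline adjustment adds about 4-11% in variance if the truncated screening score is the baseline, and 15-25% only if baseline and follow-up variances are equal. The unstated trigger, contrast and level of the t-tests are mainly missing detail. They do not show that a wrong test was used.

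**What to change.** Name one baseline-adjusted between-arm analysis as the main result for each primary outcome, and report the difference with its confidence interval.

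- **Weight:** a likelihood-based mixed model on all recorded post-baseline weights, with baseline weight, condition, session and condition x session. Use unstructured covariance, with heterogeneous first-order autoregressive as the named fallback, and a small-sample degrees-of-freedom correction. The target is the Session 8 difference.
- **Emotional eating:** ANCOVA of the Session 8 DEBQ score on the baseline score and condition. State whether the screening DEBQ serves as baseline.
- **Follow-up t-tests:** if kept, state that they are between-arm tests of change and when they run.
- **MANOVAs:** keep as supportive.

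The cost is two models on data already recorded, plus wording. The mixed model relies on missing at random, and its unstructured covariance may not converge in a small sample. The main cost is status: the Trial Design section gives dates to March 2018 and the Data Analysis section is in the past tense, so the change may come after the data were seen. If so, label it post hoc and show it beside the planned MANOVA.
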